8.15 Handling of Investigational Product

Subjects will receive one 30 ml bottle for each Part of the study. Each bottle will be used for 14 days and brought to study appointment. The bottle may be placed on the counter to be used during the treatment period.

Subjects will be asked not to subject the treatment kit to conditions which are unnatural or harmful to the product, such as excessive heat (temperatures over 77°F (25°C) and freezing temperatures (at 0°C)). Subjects may travel with their study medication but should not leave it in the hot car, outside in the cold temperatures etc. Subjects will also be asked not to tamper or cause damage to IP.

9 CONTRACEPTION REQUIREMENTS

Effective contraception is required for all women physiologically capable of becoming pregnant during study participation. Women of child-bearing potential must agree to use an acceptable form of contraception for up to 2 weeks after the study completion. Women of childbearing potential are defined as any female who has experienced menarche and who is NOT permanently sterile or postmenopausal. Postmenopausal is defined as 12 consecutive months with no menses without an alternative medical cause.

Effective contraception methods include:

- Total abstinence (when this is in line with the preferred and usual lifestyle of the study participant). Periodic abstinence (i.e., calendar, ovulation, symptothermal, postovulation methods) and withdrawal are not acceptable methods of contraception.
- Use of oral, injected or implanted hormonal methods of contraception or placement of an IUD or IUS or other forms of hormonal contraception that have comparable efficacy, for example hormone vaginal ring or transdermal hormone contraception.
- Use of barrier methods (i.e., condom, diaphragm) used with a spermicide (i.e., foam, cream, or gel that kills sperm)

In case of use of oral contraception women should have been stable on the same pill for a minimum of 90 days before the baseline visit.

Male participants of the study who are having sexual intercourse with a woman who can become pregnant must use an acceptable form of birth control while participating in the study.

Additionally, male participants are expected to let their female partners know of their participation in a research study of a drug, and that the effects of the drug on an unborn baby and on a pregnant woman are unknown. Male participants will also be expected to provide their female partners with the contraception requirements information previously described and the study doctor's contact information for questions.

Payment for all aspects of obstetrical care, child-or related care will be the study participant's responsibility.

In case of pregnancy, Investigational Product should be discontinued and the Sponsor should be informed immediately. Follow-up of the pregnancy will be mandatory until the outcome is available.

10 STUDY PROCEDURES

10.1 Screening

Prior to initiation of the recruitment phase, participating Investigator will identify a pool of potential study subjects. The Investigator will identify potentially eligible subjects in advance, by either reviewing past medical records and diagnoses, screening in clinics, referral from other physicians, or other sources of recruitment, to identify those aged 18 to 65 meeting the inclusion criteria. The accuracy of self-reported data, including height, weight and medical history, will be assessed during the initial on-site screening visit. Individuals who fail to meet study inclusion criteria will be dismissed at that time. Individuals who meet inclusion criteria will move on to on-site screening visit.

10.2 Informed Consent Procedures

Eligible participants may only be included in the study after providing a consent using the IRB-approved informed consent. Informed consent must be obtained before conducting any study-specific procedures (i.e. all of the procedures described in the protocol). The process of obtaining informed consent should be documented in the participant's source documents. The date of signing of informed consent (and withdrawal, if later withdrawn) should be documented in the eCRF.

10.3 Study Assessments

In Part 1, study assessments will occur at Baseline and Week 2 (Day 14) visit. Follow-up visit will be at Week 3 (Day 21) and Week 6 (Day 42) after treatment to perform safety assessments and clinical examination of the nasal mucosa, sinuses, and upper airway.

In Part 2, study assessments will occur at NAC titration visit (Day 0), NAC#1 visit (Day 14) and NAC#2 visit (Day 28). Preliminary efficacy assessments will be after nasal allergen challenge in a prophylaxis treatment setting.

In Part 1, subjects will be asked to report for a screening visit and if all inclusion/exclusion criteria are met, subjects will be asked to report for a baseline visit and randomization. Subjects will then be trained on the use of the nasal spray, and have their first dose of treatment on site. Subjects will remain onsite for observation for 1 hour post dosing. Subjects will then be dispensed study medication for 14 days of at home dosing. While at home, subjects will dose twice daily (am and pm), and record their dosing, any occurrence of an AE, and Total Nasal Symptom Score (TNSS) using a study diary. Subjects will be asked to visit the site at Day 14 (Week 2) and at follow-up visits at Day 21 (Week 3) and Day 42 (Week 6) for safety assessments and will additionally record Peak Nasal Inspiratory Flow (PNIF), intranasal fluid, intranasal nitric oxide (nNO) and nasal inflammation score.

In Part 2, subjects will be asked to report for a screening visit (Visit 1) and if all inclusion/exclusion criteria are met, subjects will be asked to report for a NAC titration (ragweed pollen nasal allergen titration) visit to administer a single provocative challenge dose for each subject (Visit 2). Subjects will then return 14 days after the washout period for basic health checks and baseline assessments (intranasal fluid, TNSS, PNIF, intranasal nitric oxide, and have a nasal inflammation score) followed by confirmatory NAC (NAC#1) (Visit 3). During this time subjects will use a study diary to complete TNSS at -30 (30 minutes prior to NAC), 0 (baseline prior to NAC), 15, 30, 45, 60, 90, and 120 minutes. PNIF at -30, 0, 15, 30, 60, and 120 minutes will also be obtained. TNSS is the sum of four individual symptom scores (running nose, congestion, itchy nose, and sneezing) rated on a four point scale (0-3). Subjects are required to meet the minimum qualifying TNSS score of a change of 6/12 from their baseline score, on at least 2 diary cards. Subjects will also provide samples for intranasal fluid at 0, 20, and 60 minutes, measure intranasal nitric oxide (nNO) and have a nasal inflammation score assessed by the investigator using a nasal otoscope at 0 and 120 minutes, in addition to blood collection at 120 min for biomarkers. Subjects meeting the requirement will be randomized to one of the three treatment arms. Randomization will be 1:1:1 so that equal number of subjects will be treated in each arm of the study. Subjects will then be trained on the use of the nasal spray, and have their first dose of treatment on site (self-dosing). Subjects will remain onsite for observation for 1 hour post dosing. Subjects will then be dispensed study medication for 14 days of at home dosing. While at home, subjects will dose twice daily (am and pm), and record their dosing, and any occurrence of an AE and TNSS using a study diary. Subjects will return to the clinic for the last dose following the 14 days of at home dosing for their final visit (Visit 4). During this time subjects will again have their baseline assessments and be exposed to ragweed pollen challenge (NAC#2), and will use a study diary to complete TNSS at -30, 0, 15, 30, 45, 60, 90, and 120 minutes and PNIF at -30, 0, 15, 30, 60, and 120 minutes. Prior to and 20 and 60 minutes after NAC #2, subjects will additionally provide samples for intranasal fluid, and have nNO measured and have a nasal inflammation score assessed by the investigator using a nasal otoscope at 0 and 120 min, in addition to blood collection at 120 min for biomarkers.

At the final visit for each phase of the study (Visit 5 for Part 1 and Visit 4 for Part 2), subjects may be requested to complete a subject satisfaction survey.

10.4 Inclusion Procedures

Once all inclusion/exclusion criteria are fulfilled, the patient becomes eligible for randomization and inclusion into the treatment period for each of Part 1 and Part 2 phases of the study. Treatment allocation will be performed as stated above in Section 8.5. Study medication will be delivered as stated in Section 8.7. Patients will be counseled on product application and diary completion.

10.5 Description by Type of Visit – Part 1

10.5.1 Screening Visit (Visit 1; Study Day -1) (-21 to 0 Days Visit Window)

- informed consent completed and signed
- inclusion and exclusion criteria
- demographic data
- medical/surgical history
- record concomitant medications
- obtain in clinic blood pressure, heart rate, respiratory rate
- physical exam
- body weight
- height measurement
- nasal inspection
- 12-lead ECG
- laboratory testing (blood for metabolic panel, hematology, clinical chemistry, lipid panel, liver function test, urinalysis)
- urine pregnancy test (for women of childbearing potential)
- safety AEs
- study diary

10.5.2 Baseline ABPM Placement (-3 to 0 Days Visit Window)

This visit should occur 24 hours prior to baseline visit (Visit 2) between the hours of 8am +/- 2 hrs.

- obtain in clinic blood pressure and heart rate
- provide 24 hr ABPM device to the subject
- train the subject on the use of the machine and provide instructions

10.5.3 Baseline Visit (Visit 2; Study Day 0) (-3 to 1 Days Visit Window)

This visit should occur between the hours of 8am +/- 2 hrs.

- inclusion and exclusion criteria
- medical/surgical history
- record concomitant medications
- obtain in clinic blood pressure, heart rate, respiratory rate (pre- and post-first dose)
- physical exam
- ambulatory blood pressure monitoring (ABPM) removal (after 24 hour measurement) and evaluation of technical success/failure criteria
- randomization
- nasal inspection (pre- and post-first dose)
- delivery of the corresponding pack of Investigational Product
- Investigational Product application (under medical supervision)
- obtain study medication weight for Investigational Product compliance
- study counseling

- safety AEs
- nasal fluid collection for biomarkers
- blood collection for biomarkers
- peak nasal inspiratory flow (PNIF)
- intranasal nitric oxide
- nasal inflammation score
- study diary

10.5.4 Baseline Repeat ABPM Placement (if Necessary) (-3 to 1 Days Visit Window)

If the ABPM technical acceptance criteria are not met during the baseline visit (Visit 2) reading, the ABPM session may be repeated. In the event of technical failure, study coordinators will not perform any study related activities outlined in Visit 2 prior to repeating the ABPM session.

Repeat monitoring may be scheduled up to 48 hours after the failed monitoring.

This visit should occur between the hours of 8am +/- 2 hrs.

- provide 24 hr ABPM device to the patient
- train the patient on the use of the machine and provide instruction

The patient will come back 24 hours later to remove ABPM machine and check on the readings to make sure the equipment performed as expected.

If the machine performed as expected, then Visit 2 activities will be performed as outlined in the section above.

10.5.5 Week 2 ABPM Placement (± 3 Days Visit Window)

This visit should occur 24 hours prior to week 2 visit (Visit 3) between the hours of 8am +/- 2 hrs.

- obtain in clinic blood pressure and heart rate
- provide 24 hr ABPM device to the subject
- train the subject on the use of the machine and provide instructions

10.5.6 Week 2 Visit (Visit 3; Study Day 14) (± 3 Days Visit Window)

- record concomitant medications
- obtain in clinic blood pressure, heart rate, respiratory rate
- physical exam
- body weight
- ABPM removal (after 24 hour measurement) and evaluation of technical success/failure criteria
- nasal inspection
- 12-lead ECG

- Investigational Product application (last dose, if needed)
- obtain study medication weight for Investigational Product compliance
- laboratory testing (blood for metabolic panel, hematology, clinical chemistry, lipid panel, liver function test, urinalysis)
- safety AEs
- nasal fluid collection for biomarkers
- blood collection for biomarkers
- peak nasal inspiratory flow (PNIF)
- intranasal nitric oxide
- nasal inflammation score
- study diary

10.5.7 Week 2 Repeat ABPM Placement (if Necessary) (± 3 Days Visit Window)

If the ABPM technical acceptance criteria are not met during the week 2 visit (Visit 3) reading, the ABPM session may be repeated. In the event of technical failure, study coordinators will not perform any study related activities outlined in Visit 3 prior to repeating the ABPM session.

Repeat monitoring may be scheduled up to 48 hours after the failed monitoring.

This visit should occur between the hours of 8am +/- 2 hrs.

- provide 24 hr ABPM device to the patient
- train the patient on the use of the machine and provide instruction

The patient will come back 24 hours later to remove ABPM machine and check on the readings to make sure the equipment performed as expected.

If the machine performed as expected, then Visit 3 activities will be performed as outlined in the section above.

10.5.8 Follow-up #1 Visit (Visit 4; Study Day 21) (± 3 Days Visit Window)

- record concomitant medications
- obtain in clinic blood pressure, heart rate, respiratory rate
- physical exam
- body weight
- nasal inspection
- safety AEs
- peak nasal inspiratory flow (PNIF)
- intranasal nitric oxide
- nasal inflammation score
- study diary

10.5.9 Follow-up #2 Visit (Visit 5; Study Day 42) (± 3 Days Visit Window)

- record concomitant medications
- obtain in clinic blood pressure, heart rate, respiratory rate
- physical exam
- body weight
- nasal inspection
- 12-lead ECG
- laboratory testing (blood for metabolic panel, hematology, clinical chemistry, lipid panel, liver function test, urinalysis)
- safety AEs
- nasal fluid collection for biomarkers
- blood collection for biomarkers
- peak nasal inspiratory flow (PNIF)
- intranasal nitric oxide
- nasal inflammation score
- study diary
- subject satisfaction survey

10.6 Description by Type of Visit – Part 2**10.6.1 Screening Visit (Visit 1; Study Day -1) (-21 to 0 Days Visit Window)**

- informed consent completed and signed
- inclusion and exclusion criteria
- demographic data
- medical/surgical history
- record concomitant medications
- obtain in clinic blood pressure, heart rate, respiratory rate
- physical exam
- body weight
- height measurement
- allergen skin test (skin prick test) (if documentation of a positive test within the past 12 months is not available)
- blood collection for IgE (if documentation of a positive test within the past 12 months is not available)
- nasal inspection
- laboratory testing (blood for metabolic panel, hematology, clinical chemistry, lipid panel, liver function test, urinalysis)
- urine pregnancy test (for women of childbearing potential)
- safety AEs
- study diary

10.6.2 NAC Titration Visit (Visit 2; Study Day 0) (± 3 Days Visit Window)

- physical exam
- nasal inspection
- NAC
- safety AEs
- peak nasal inspiratory flow (PNIF) (to be completed pre (-30 and 0 min) and post NAC (15, 30, 60, and 120 min))
- intranasal nitric oxide
- nasal inflammation score
- study diary (TNSS to be completed pre (-30 and 0 min) and post NAC (15, 30, 45, 60, 90, and 120 min))

10.6.3 NAC #1 Visit (Visit 3; Study Day 14) (± 3 Days Visit Window)

- record concomitant medications
- obtain in clinic blood pressure, heart rate, respiratory rate
- physical exam
- body weight
- randomization
- nasal inspection
- NAC
- delivery of the corresponding pack of Investigational Product
- Investigational Product application (under medical supervision)
- obtain study medication weight for Investigational Product compliance
- study counseling
- safety AEs
- nasal fluid collection for biomarkers (to be completed pre (0 min) and post NAC (20 and 60 min))
- blood collection for biomarkers (to be completed post NAC)
- peak nasal inspiratory flow (PNIF) (to be completed pre (-30 and 0 min) and post NAC (15, 30, 60, and 120 min))
- intranasal nitric oxide (to be completed pre (0 min) and post NAC (120 min))
- nasal inflammation score (to be completed pre (0 min) and post NAC (120 min))
- study diary (TNSS to be completed pre (-30 and 0 min) and post NAC (15, 30, 45, 60, 90, and 120 min))

10.6.4 NAC #2 Visit (Visit 4; Study Day 28) (± 3 Days Visit Window)

- record concomitant medications
- obtain in clinic blood pressure, heart rate, respiratory rate
- physical exam
- body weight
- nasal inspection

- NAC
- Investigational Product application (last dose, if needed)
- obtain study medication weight for Investigational Product compliance
- laboratory testing (blood for metabolic panel, hematology, clinical chemistry, lipid panel, liver function test, urinalysis)
- safety AEs
- nasal fluid collection for biomarkers (to be completed pre (0 min) and post NAC (20 and 60 min))
- blood collection for biomarkers (to be completed post NAC)
- peak nasal inspiratory flow (PNIF) (to be completed pre (-30 and 0 min) and post NAC (15, 30, 60, and 120 min))
- intranasal nitric oxide (to be completed pre (0 min) and post NAC (120 min))
- nasal inflammation score (to be completed pre (0 min) and post NAC (120 min))
- study diary (TNSS to be completed pre (-30 and 0 min) and post NAC (15, 30, 45, 60, 90, and 120 min))
- subject satisfaction survey

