8.7 Treatment Application

Subjects will receive one 30 ml bottle at the Baseline visit (Visit 2) for a 14 day application in Part 1. Subjects will receive one 30 ml bottle at the NAC #1 visit (Visit 3) for a 14 day application in Part 2. Subjects will be instructed in the use of the spray bottle and asked to self-administer the Investigational Product as follows:

- ☒ Spray 1 pump of medication into each nostril twice a day for 14 days

Detailed Investigational Product nasal spray instructions are as follows:

- Shake bottle gently
- Prime nozzle if unused; Pump until mist appears (5 times)
- Place nozzle straight up one nostril and pump once
- Sniff gently after spraying
- Repeat other nostril
- Wipe spray nozzle with tissue when done
- Do not wash/rinse the application site or blow their nose *for 30 min* after applying the mist

In Part 1, subjects will be asked to report for a screening visit and if all inclusion/exclusion criteria are met, subjects will be asked to report for a baseline visit and randomization. Subjects will then be trained on the use of the nasal spray, and have their first dose of treatment on site. Subjects will remain onsite for observation for 1 hour post dosing. Subjects will then be dispensed study medication for 14 days of at home dosing. While at home, subjects will dose twice daily (am and pm), and record their dosing, any occurrence of an AE, and Total Nasal Symptom Score (TNSS) using a study diary. Subjects will be asked to visit the site at Day 14 (Week 2) and at follow-up visits at Day 21 (Week 3) and Day 42 (Week 6) for safety assessments and will additionally record Peak Nasal Inspiratory Flow (PNIF), intranasal fluid, intranasal nitric oxide (nNO) and nasal inflammation score.

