11.5.2 Office Visit

Subjects must arrive at the office for ABPM hookup NOT HAVING TAKEN that day's dose of study medication, and at an appropriate time so that ABPM hookup, dosing of study medication, and start of the ABPM test is at 8 am +/- 2 hrs (window 6:00 am – 10:00 am) following the guidelines below. Subjects who are non-compliant will be rescheduled for the following day or later within the visit window.

- Subject dosing of study medication must occur no earlier than 6:00 AM and no later than 10:00 AM.
- There should be at least one (1) manually initiated ABPM reading after dosing of study medication. If no manual post-dose reading was recorded, START TEST time will equal the 1st valid reading after dosing, provided that the reading occurs between 6:00 am and 10:00 am.
- There should be a final manual reading on or after 24 hours of recording. If a manual reading was not recorded, the first recording after 24 hours will be considered the last valid recording of the session.

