11.5.5 Repeat ABPM

If the ABPM technical acceptance criteria are not met the ABPM session may be repeated. Repeat monitoring may be scheduled up to 48 hours after the failed monitoring.

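### For a Visit 3 on Day 14 or later, a failed Week 2 ABPM holds back every Visit 3 assessment until a repeat that ends past the 14-day course, with no route if the repeat fails or is not done

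*Protocol*

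**What the plan says.** Protocol 10.5.6 sets Visit 3 of Part 1 at Day 14 ±3 days. Its list covers clinic blood pressure, heart rate and respiratory rate, physical exam, nasal inspection, ECG, safety laboratory tests, AE review, nasal fluid and blood biomarkers, PNIF, nasal nitric oxide and nasal inflammation score. It also covers a last dose if one is needed, weighing of the study medication, and removal and technical check of the ABPM device.

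Protocol 10.5.7, also headed ±3 days, covers a failed recording:
- the repeat is optional: "If the ABPM technical acceptance criteria are not met during the week 2 visit (Visit 3) reading, the ABPM session may be repeated";
- the other activities wait: "study coordinators will not perform any study related activities outlined in Visit 3 prior to repeating the ABPM session";
- timing, repeated in 11.5.5: "Repeat monitoring may be scheduled up to 48 hours after the failed monitoring";
- duration: "The patient will come back 24 hours later to remove ABPM machine and check on the readings";
- release of the held activities: "If the machine performed as expected, then Visit 3 activities will be performed as outlined in the section above".

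The baseline section, 10.5.4, carries the same hold: "study coordinators will not perform any study related activities outlined in Visit 2 prior to repeating the ABPM session".

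On dosing, 8.7 says "Spray 1 pump of medication into each nostril twice a day for 14 days". Section 11.5.2 says "Subjects must arrive at the office for ABPM hookup NOT HAVING TAKEN that day's dose of study medication", and then has the subject dosed at the hookup with a reading taken after the dose.

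Section 11.5.4 keeps a subject who passes at baseline but fails the final repeat in the clinic blood pressure analysis, drops that subject from the ABPM analysis, and expects this in under 5% of patients. SAP 2.8 analyses visits as recorded, with no split by time since last dose.

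**The concern.** At baseline the hold has a visible purpose: the first dose is a Visit 2 activity, so waiting secures a valid recording before any drug is given. At Week 2 the subject has already been dosed for about two weeks, and the protocol gives no reason for carrying the hold over.

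The consequence is that an equipment fault in a measure not named in the primary endpoint (4.1: AEs, physical exam, vital signs) postpones measures that are. It also postpones the only ECG and safety laboratory tests scheduled between screening and Day 42. For a visit on Day 14 or later, these move past the end of treatment but keep the Week 2 label. If the repeat fails or is never done, 10.5.7 has no step that releases them at all. The two-week safety data are what the internal safety committee reviews before Part 2 (12.5), so gaps or mislabelled timing there matter more than the subject count alone suggests.

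**Working it through.** No figure in the plan needs reproducing; the check is calendar arithmetic and a reading of the branches.

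**Inputs.** First dose on Day 0 and a 14-day course (8.7, 10.5.3). Visit 3 on Day 11 to 17 (10.5.6). The failed session ends at Visit 3. Restart 0 to 2 days later and a 24-hour recording (10.5.7). Part 1 has 24 subjects, 8 per active dose (14.1).

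**Day on which the held assessments are done** = Visit 3 day + restart delay (0 to 2) + 1.

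| Visit 3 day | Assessments done on | Relative to Day 14 |
|---|---|---|
| 11 | 12 to 14 | all by Day 14 |
| 12 | 13 to 15 | mixed |
| 13 | 14 to 16 | mixed |
| 14 (nominal) | 15 to 17 | all after |
| 15 | 16 to 18 | all after |
| 16 | 17 to 19 | all after |
| 17 | 18 to 20 | all after |

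Days 18 to 20 lie outside the ±3-day window in the headings of 10.5.6 and 10.5.7. If the 48 hours are read as the time to finish the repeat rather than start it, each upper bound falls by one day, so the nominal visit gives Day 15 to 16.

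**Dosing in the gap.** The course is 14 × 2 = 28 doses, or 29 if the on-site dose is added to 14 days at home. If twice-daily dosing ran on to the morning of Day D, the total would be 2D + 1: 31, 33 or 35 for Day 15, 16 or 17, which is 2, 4 or 6 more than 29. If dosing stopped, a repeat hooked up on a later day would start without the dose that 11.5.2 calls for. No section says which applies, and the last dose is itself among the activities held.

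**Branches of 10.5.7.**
- Repeat done and successful: assessments released, 1 to 3 days late.
- Repeat done and failed: no instruction. Section 11.5.4 nevertheless expects clinic blood pressure data from this subject. On its estimate this is under 0.05 × 24 = 1.2 subjects.
- No repeat, which the wording permits: no instruction.

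**How many subjects.** The first-session failure rate is not given. For an assumed rate p, expected failures are 24p and the chance of at least one is 1 − (1 − p)^24:
- p = 5%: 1.2 subjects, 71%;
- p = 10%: 2.4 subjects, 92%;
- p = 20%: 4.8 subjects, 99.5%.

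Each affected subject on active treatment is 1 of 8, or 12.5%, of that dose group.

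**The case against.** A reader might infer that every repeat falls after the course and that the Part 1 primary safety data as a whole become off-treatment. The documents do not support that:
- The repeat is optional, and a Visit 3 on Day 11 always leaves room to finish by Day 14; Days 12 and 13 sometimes do.
- Clinic blood pressure and heart rate are taken at the Week 2 placement visit the day before Visit 3 (10.5.5), before any failure is known. Baseline adds vital signs and nasal inspection after the first dose (10.5.3).
- AEs are recorded daily in the diary, and SAP 2.4.1 defines treatment emergence by onset, so a late review reclassifies nothing.
- The primary endpoint includes follow-up, and ECG and laboratory tests are not named in it.

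Nor do the documents force a choice between extra dosing and an undosed recording in every case. A repeat hooked up on Day 14 itself could use a dose taken that day; the conflict arises when hookup falls later. The hold might also be meant to keep all Week 2 measures on one day, or to avoid completing the last dose and the weighing before a repeat that calls for a dose. And the +3-day window already allows a late Visit 3 without any ABPM failure.

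All of this narrows the point. It does not explain why the physical exam, respiratory rate, ECG and laboratory tests must wait on the device, and it does not supply the missing branches. The placement reading might be used to satisfy 11.5.4, but no section says so, and it includes no respiratory rate, exam, ECG or laboratory result.

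**Conclusion.** The point holds in a limited form. For a Visit 3 on Day 14 or later, 10.5.7 moves every Visit 3 assessment past the end of the 14-day course: to Day 15 to 17 from the nominal visit, with anything later outside the window. What has no near-Visit 3 substitute is the physical exam, respiratory rate, nasal inspection, ECG and laboratory tests, and these would be summarised as Week 2. Read literally, a subject with a failed repeat or no repeat has no Visit 3 assessments, which is at odds with 11.5.4. Dosing status during a repeat hooked up after Day 14 is not stated and does not fit 8.7 and 11.5.2 together.

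About 1 to 5 of 24 subjects would be affected. That range rests entirely on an assumed 5% to 20% first-session failure rate. How much any effect would fade over 1 to 3 days off drug cannot be judged, because the documents give no offset data. The change is worth making but is not critical.

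**What to change.** - In 10.5.7, limit the hold so that the non-dosing Visit 3 assessments are done at Visit 3 as scheduled whatever the ABPM result, and only the ABPM is repeated. This also closes the gap for a failed or omitted repeat. The baseline hold in 10.5.4 is not affected.
- Record the time since last dose for the Visit 3 measurements and any repeat ABPM, and have the SAP flag Week 2 values taken off treatment. The flag also covers a Visit 3 that is late only because of the +3-day window.
- Reconcile 8.7, 10.5.6, 10.5.7, 11.5.2 and 11.5.4 on dosing status during a Week 2 repeat, including the last dose and the weighing. Which dosing rule should apply is for the sponsor and investigators to settle; no position is taken here.

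The cost is a short amendment, one eCRF field and a line in the SAP. The downside is that, in the few repeat cases, the ABPM and the other Week 2 measures fall on different days.
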